### **Dose-Expansion Cohorts**

Once the RP2D is reached, a total of10 patients will be treated at this dose. For the expansion cohort, patients will continue to be monitored for occurrence of DLT. If 2 of the first 5 patients or if  $\geq$  2 of 6 patients experience DLT, the PI will discuss with all study investigators and with CTEP whether further addition of patients is needed to reassess the RP2D.

Monitoring of safety and toxicity data will be captured in OnCore, Moffitt's clinical trials database.

Dose-limiting toxicities are defined as any of the following that is at least possibly attributable to the investigational treatment:

- 1. Grade 2-4 infusion toxicity
- 2. Grade 4 organ toxicity (as defined by NCI CTCAE v 5.0), not preexisting, not due to the primary malignancy, and not due to chemotherapy or infection
- 3. Grade 3 organ toxicity that does not resolve within 14 days and that is not preexisting, not due to the primary malignancy, and not due to chemotherapy or infection
- 4. Grade 2-4 acute GvHD
- Delayed neutrophil recovery: ANC >500/μl does not occur within 56 days AND measurable donor chimerism is >5%
- 6. Grade 3-4 cytokine release syndrome (CRS) (see Appendix C) (75)
  Any grade 5 reaction other than progressive disease

### 6.2 PREPARATION/HANDLING/STORAGE/ACCOUNTABILITY

# 6.2.1 ACQUISITION AND ACCOUNTABILITY

Donors will have their blood collected via peripheral whole blood collection (450 ml into CPDA-1) or a leukapheresis procedure will be performed to collect mononuclear cells under steady state conditions (without mobilization). Each leukapheresis collection will be performed using institutional standard operating procedures for MNC collection. The method of blood donation, phlebotomy versus leukapheresis, will be determined by prior to donation and based on the volume of blood required to obtain the targeted CD4+T cell dose.

# 6.2.2 FORMULATION, APPEARANCE, PACKAGING, AND LABELING

T Cells, Apheresis: CD8 Reduced and T Cells, Whole Blood: CD8 Reduced products are cell suspensions collected from allogeneic donors; the product is characterized by flow analysis (CD4+ cells and CD8+ cells). The product is

free of bacterial contamination as determined by gram stain analysis and is formulated in an infusion compatible solution. The T Cells, Apheresis: CD8 Reduced and T Cells, Whole Blood: CD8 Reduced products are provided as a fresh cell suspension. The product is a sterile suspension of mononuclear cells. If the cells will not be infused immediately, they may be suspended in preservation medium (e.g., HypoThermosol®). The volume in the bag will vary depending on the number of cells. Cell concentrations will be between 5x10^7 cells/ml to 1x10^8 cells/ml. The cells should be stored in a monitored 2-8°C refrigerator until ready for use.

# 6.2.3 PRODUCT STORAGE AND STABILITY

T Cells, Apheresis: CD8 Reduced and T Cells, Whole Blood: CD8 Reduced products are stored at 2-8°C until the time of use. The refrigerator units at clinical sites must be located in a controlled-access facility with an alarm monitoring system.

Products are shipped according to established SOPs, FACT Standards and DOT regulations. Fresh product shipments are monitored with single trip data logger to provide continuous temperature monitoring.

T Cells, Apheresis: CD8 Reduced and T Cells, Whole Blood: CD8 Reduced products should not be allowed to warm above 15°C during transport. A study was performed at Johns Hopkins University to evaluate the post-processing stability of T Cells, Apheresis: CD8 Reduced products (unpublished). Cell viability, as measured by trypan blue dye exclusion, was ≥88% for up to 72 hours after storage.

### 6.2.4 PREPARATION

T Cells, Apheresis: CD8 Reduced and T Cells, Whole Blood: CD8 Reduced products are cells that remain in an apheresis or whole blood product after depletion of CD8+ cells using the CliniMACS® system with the CliniMACS® CD8 reagent. The product is a sterile suspension of mononuclear cells suspended in HypoThermosol® or similar preservative. The volume in the bag will vary depending on the number of cells. Cell concentrations will be between 5x10^7 cells/ml to 1x10^8 cells/ml.

After manufacturing, the product is stored or shipped at 2-8°C prior to infusion. T Cells, Apheresis: CD8 Reduced and T Cells, Whole Blood: CD8 Reduced products should not be allowed to warm above 15°C during transport.

Product infusion should follow established SOPs.

#### 6.3 MEASURES TO MINIMIZE BIAS: RANDOMIZATION AND BLINDING

This is a single arm study. Patients will be treated in order of enrollment at the current dose level as delineated in the dose escalation schema. Neither the patients nor the trial physicians/providers will be blinded as all patients on trial will receive the same intervention. However, the final analysis will use de-identified raw data.

#### 6.4 STUDY INTERVENTION COMPLIANCE

Data and safety monitoring will follow institutional protocol. Additionally, scheduled meetings will take place monthly and will include the protocol PI, clinical trial coordinator, and, when appropriate, the collaborators, subinvestigators, and biostatistician involved with the conduct of the protocol.

During these meetings the investigators will discuss matters related to: safety of protocol participants, validity and integrity of the data, enrollment rate relative to expectation, characteristics of participants, retention of participants, adherence to protocol (potential or real protocol violations), data completeness, and progress of data for secondary objectives.

Regulatory documents and case report forms will be monitored internally according to Moffitt Cancer Center Monitoring Policies. Monitoring will be performed regularly by the MCC Clinical Monitoring Core for accuracy, completeness, and source verification of data entry, validation of appropriate informed consent process, reporting of SAEs, and adherence to the protocol, Good Clinical Practice (GCP) guidelines, and applicable regulatory requirements. The Moffitt Protocol Monitoring Committee (PMC) meets monthly and reviews accrual, patterns and frequencies of all adverse events, protocol violations and when applicable, internal audit results.

# 6.5 CONCOMITANT THERAPY

Patients enrolled on this study may not be concurrently enrolled on another interventional therapeutic clinical trial.

#### 6.5.1 RESCUE MEDICINE

The study site will supply the rescue medication tocilizumab for the management of cytokine release syndrome (CRS). This rescue medicine will be obtained locally. Although the use of rescue medications is allowable at any time during the study, the use of rescue medications should follow the algorithm for treatment of CRS as described in Appendix C. The date and time of rescue medication administration as well as the name and dosage regimen of the rescue medication must be recorded.

# 7 STUDY INTERVENTION DISCONTINUATION AND PARTICIPANT DISCONTINUATION/WITHDRAWAL

#### 7.1 DISCONTINUATION OF STUDY INTERVENTION

Discontinuation from NE-DLI does not mean discontinuation from the study, and remaining study procedures should be completed as indicated by the study protocol. If a clinically significant finding is identified (including, but not limited to changes from baseline) after enrollment, the investigator or qualified designee will determine if any change in participant management is needed. Any new clinically relevant finding will be reported as an AE.

The data to be collected at the time of study intervention discontinuation will include the following:

- Cause of discontinuation
- Most recent laboratory values
- Evidence of adverse events
- Disease status at the time of discontinuation

#### 7.2 PARTICIPANT DISCONTINUATION/WITHDRAWAL FROM THE STUDY

Patients may elect to withdraw from the study at any point without any further justification.

Additionally, patients may be removed from the study at the discretion of their medical providers on the basis of the following criteria:

- Adverse events or any concern that continuing in the study would be harmful
- Need for treatment not allowed in the study, including disease relapse while on study
- Failure by a patient to comply with study protocol
- Onset of pregnancy after enrolling in the study
- Cancellation of the study

#### 7.3 LOST TO FOLLOW-UP

A participant will be considered lost to follow-up if he or she fails to return for 3 scheduled visits and if study site staff is unable to contact the participant.

The following actions must be taken if a participant fails to return to the clinic for a required study visit:

- The site will attempt to contact the participant and reschedule the missed visit for 1 month and counsel
  the participant on the importance of maintaining the assigned visit schedule and ascertain whether the
  participant wishes to and/or should continue in the study.
- Before a participant is deemed lost to follow-up, the investigator or designee will make every effort to
  regain contact with the participant (where possible, by making 3 telephone calls and, if necessary, by
  sending a certified letter to the participant's last known mailing address or local equivalent methods).
   These contact attempts should be documented in the participant's medical record or study file.
- A minimum of 2 years should be spent attempting to locate the patient. If after that period of time the
  coordinator has sufficiently documented all failed attempts to locate the patient, including sending a
  certified letter with no response, then he or she will be considered to have withdrawn from the study for
  the primary reason of being lost to follow-up.

# 8 STUDY ASSESSMENTS AND PROCEDURES

# 8.1 SAFETY ASSESSMENTS

Safety assessments will be as follows:

- History and physical: Initial and repeated at days 42 and 56, 6 months, and 1 year to evaluate for subjective or exam findings consistent with AEs.
- Bone marrow biopsy: Day 42 to evaluate the efficacy of the intervention. Day 42 bone marrow biopsy may
  be performed earlier than the day 42 if the subject has recovered from aplasia, defined as recovery of the
  ANC >500/μl.
- Peripheral blood and bone marrow chimerism: To rule out donor engraftment and confirm rejection of the
  DLI product, donor cell chimerism will be measured after neutrophil recovery (ANC ≥ 500/µI) or on day 42
  +/- 3 days after infusion. Engraftment is necessary for GVHD, so product rejection increases the long term
  safety of the product.
- Complete blood count (CBC): 3 times per week until ANC recovers to 500. Weekly through day 56. This assessment is necessary to monitor for hematologic toxicity.
- Comprehensive metabolic panel (CMP): Weekly through day 56 to evaluate for toxicity to the liver, kidneys, or electrolyte derangements.

- C Reactive Protein (CRP) and Ferritin: Weekly through day 56 to screen for evidence of cytokine release syndrome (CRS)
- Cytomegalovirus polymerase chain reaction (PCR): Weekly through day 56 to monitor for CMV reactivation while awaiting immune reconstitution.

	Initial	Allowable time from start of induction	Starting Day 0	Day 28	Day 42	Day 56	6 months +/- 2 weeks	1 yr +/- 2 weeks
History and physical	Х	Within 30 days			Х	Х	X	Х
Performance status	Х	Within 30 days						
Staging Bone Marrow Biopsy and aspirate for research	Х	Within 30 days			Xa			
Peripheral blood for research	Х		Daily days 0-7		Xa			
CBC & Diff	×	Within 7 days	ANC<500- 3x/week  ANC≥500- weekly to day 56		×	×	х	х
СМР	Х	Within 7 days	Weekly to day 56		Х	Х	Х	Х
CXR or Chest CT	Χ	Within 30 days						
Pregnancy test (women, childbearing age)	Х	Within 30 days						
Human Immunodeficiency Virus	Х	Within 30 days						
EKG	Х	-						
MUGA or ECHO	Χ	Within 30 days						
HLA typing	Х							
Anti-donor HLA antibody testing	Х				Х			
Adverse Event Monitoring			Weekly to day 56		Х	Х	X	Х
GvHD evaluation			At onset, weekly until resolves		х	х		
Peripheral blood or bone marrow for donor chimerism			If suspected GvHD		Xa	Xp		
CMV IgG	X	Within 30 days						
CMV PCR			Weekly through day 56					
C Reactive Protein	Х	Within 7 days	Weekly through day 56					
Ferritin	X	Within 7 days	Weekly through day 56		х	Х		

Abbreviations: ANC, absolute neutrophil count; CBC, complete blood count; CMP, comprehensive metabolic panel; CMV, cytomegalovirus; CXR, chest radiograph; CT, computerized tomography scan; diff, differential blood count; ECHO, echocardiogram; EKG, electrocardiogram; GvHD, graftversus-host disease; MUGA, multigated acquisition; PCR,, polymerase chain reaction

Tracking of days begins from day of cell transfusion (eg, Day 56 is 56 days after initial cell infusion). Day of cell transfusion is marked as Day 0. Procedures can be performed ± 3 days from marked date, unless otherwise specified. a Specified day 42 samples may be performed prior to day 42 if the patient has

recovered from aplasia, defined as ANC >500/ $\mu$ l. Otherwise, the specimen collections will be planned for day 42 +/-3 days. bDay 56 chimerism measurement may be omitted if donor T-cell chimerism is < 5% on first measurement or if whole blood/marrow chimerism is < 5%. If donor chimerism >5% on day 56, then the investigator will continue measuring monthly until it decreases to <5% or until 1 year, whichever comes first.

Pre-treatment research samples may be added on to previously collected samples (e.g., Moffitt Total Cancer Care) in lieu of collecting new samples. Screening tests obtained as standard of care prior to patient consent to this trial may be used for screening purposes if the tests fall within the allowable time window to the start of induction chemotherapy as defined in the table above.

NOTE: In certain clinical circumstances (e.g. relapsed or terminally ill patients, risk of undue harm to patients, etc.) study tests may be omitted at the physician's discretion. Additionally, tests may be rescheduled as clinically indicated.

#### 8.2 OTHER ASSESSMENTS

Baseline evaluations to be performed within 30 days of initiating treatment:

- Performance status: to confirm ECOG <2

- Chest X-ray or Chest CT: To rule out active pulmonary infection
- EKG and either MUGA or echocardiogram: To confirm adequate cardiac function
- HIV testing: To rule out active HIV infection which would require treatment prior to initiating chemotherapy
- Pregnancy testing: To rule out pregnancy as participation in this study may be dangerous to the fetus
- Bone marrow biopsy: To confirm diagnosis and evaluate baseline disease status
- CMV IgG: To allow for optimal, CMV matched donor selection

Baseline evaluations to be performed anytime prior to enrollment:

 HLA typing with anti-donor HLA antibody testing: To determine if this treatment increases production of anti-HLA antibodies.

Baseline evaluations to be performed within 7 days of initiating therapy:

- CBC: To confirm adequate hematologic parameters to proceed on study
- CMP: To confirm adequate kidney/liver function to proceed on study
- CRP and Ferritin: To risk stratify risk of cytokine release syndrome prior to treatment

CMV PCR: To rule out active CMV infection and assist with donor selection.

NOTE: In certain clinical circumstances (e.g. relapsed or terminally ill patients, risk of undue harm to patients, etc.) study tests may be omitted at the physician's discretion. Standard of care tests may be rescheduled as clinically indicated.

# 8.3 BIOMARKER, CORRELATIVE, AND SPECIAL STUDIES OR OTHER ENDPOINTS

Specimen Type	Baseline (Pre- treatment)	Days 0-7*	Day 42**
Peripheral blood sample	X	Daily	Х
Bone marrow biopsy/aspirate	Х		Х

\* Research sample collection may be omitted if the day falls on a weekend or holiday.

#### 8.3.1 PLANNED CORRELATIVE STUDIES

Below are outlined correlative studies to be completed from the tissue samples. These will be performed as funding permits. Specific reagents and devices may be substituted for equivalent reagents/devices as available to the performing laboratory.

Hypothesis: In patients with MDS/AML, allogeneic HLA-mismatched CD4+ DLI will result in reversal of immune exhaustion of recipient tumor specific CD8+ T cells.

# Aim 1: Determine if treatment of MDS/AML with HLA-mismatched CD4+ DLI results in reversal of expression of protein markers of immune exhaustion in recipient cytotoxic T cells.

#### Markers of Immune Exhaustion

Immune exhaustion is characterized by CD8+ T cell surface expression of inhibitory proteins such as PD-1, which contribute to treatment failure in MDS.(14, 36, 76-78) Thus, we wish to assess whether HLA-mismatched CD4+ DLI can reverse expression of negative immune checkpoints on exhausted CD8+ T cells in patients with MDS who failed standard therapy. All enrolled patients will have peripheral blood and bone marrow samples obtained at baseline prior to protocol chemotherapy, and at the time of hematologic recovery, 30-50 days after HLA-mismatched CD4+ DLI. Peripheral blood mononuclear cells (PBMCs) and bone marrow mononuclear cells (BMMCs) will be enriched using standard FicoII-Hypaque methods. The cells will be stained with propidium lodide/acridine orange and live cells will be counted using a Cellometer 2000 automated cell counter (Nexcelom Biosciences, Lawrence, MA). The cells will be suspended in Recovery Freeze Medium (Invitrogen, Carlsbad, CA) and controlled rate frozen to -80°C before transfer to liquid nitrogen storage. In batch, baseline and post-treatment samples will be thawed, followed by isolation of CD4+ and CD8+ populations using MultiSort magnetic MicroBeads (Miltenyi Biotec, Gaithersburg, MD). For this CD4+ cells will be bead captured on one column and the flow through will be mixed with CD8 beads and then captured on a second column. Total RNA will be extracted from one million each of the isolated

\*\*May be obtained earlier than day 42 if ANC recovery to >500/uL. (See study calendar)

CD4+ and CD8+ cells and stored for subsequent RNAseq analysis. The collected samples will be analyzed via multicolor flow cytometric assay to characterize expression of markers of immune exhaustion (TIM3, LAG-3, PD1, PDL1, CTLA4).(79-81) Pre-treatment and post-treatment values will be compared to determine if expression of exhaustion antigens is down regulated after HLA-mismatched CD4+ DLI therapy, thus predicting that immune exhaustion is reversed. The one-sample t-test will be used to assess if the markers are significantly changed after treatment.

#### Host versus Donor Origin of CD8+ T Cells

Because we hypothesize that reversal of immune exhaustion will specifically occur in the recipient's cytotoxic T cells, we wish to identify if reinvigorated CD8+ T cells are derived from the donor or the host as donor derived CD8+ T cells would be expected to lead to engraftment and potentially GVHD. Since the CD4+ DLI is intentionally HLA mismatched, RNA sequencing can be used to distinguish and quantify donor versus recipient HLA types in the samples.(82) We will isolate the tumor infiltrating cells in the marrow after HLA-mismatched CD4+ DLI and use RNA sequencing of HLA to determine if the cells are donor- or host-derived. We will supplement this testing with standard clinical bone marrow chimerism studies. In combination, these tests will assess whether donor CD4+ T cells are rejected and will confirm that the immune competent CD8+ T cells are of host origin.

# Aim 2: In patients with MDS/AML who received HLA-mismatched CD4+ DLI therapy, characterize anti-leukemic activity and specificity of recipient marrow CD8+ T cells in response to HLA-mismatched CD4+ DLI.

#### Leukemia-Specific Cytolytic Activity of CD8+ T cells

After treatment with HLA-mismatched CD4+ DLI, we anticipate a reversal of immune exhaustion and a subsequent host-versus-leukemia response. We will evaluate changes to cytolytic activity of the recipient cytotoxic CD8+ T cells before and after therapy, first, in cytotoxicity experiments at different effector:target (CTL:tumor cell) ratios using leukemia blasts collected from the pre-treatment samples. If the frequencies of tumor-reactive T cells required more sensitive methods, we would use ELISPOT testing. Specifically, this sensitive assay can quantify a successful response to HLA-mismatched CD4+ DLI characterized by an increase in the frequencies of CD8+ T cells secreting interferon-γ (IFN-γ) in response to cognate tumor antigen, using peripheral or BM malignant cells as targets.(83) Cytotoxicity and/or ELISPOT results will be compared between patients who achieve a remission and those who do not to show that clinical response is dependent on marrow infiltration by activated cytotoxic T cells. The Satterthwaite ttest will be used to detect a significant difference in changes to cytolytic activity and increase in frequency of CD8+ T-cells before and after treatment, and between patients who achieve a remission and those who do not. The odds ratio will be estimated along with 95% confidence intervals by using the simple logistic regression or the generalized estimating equation (GEE) model. Building multivariable model will not be considered due to the small sample size issue. The data transformation (e.g., log2-transformation) may be considered to meet the normality assumption for the application of parametric analytic tools. The Wilcoxon singed-rank test or Wilcoxon rank-sum test may be considered as the secondary approaches if necessary. As this is an exploratory study, the multiplicity adjustment is not considered.

#### Clonotype of Expanded CD8+ T cells

We will assess whether these activated, tumor specific, cytotoxic T cells are clonal. In the post-allogeneic transplant setting, prior studies have shown that response to CD8+ depleted DLI is most successful when there is a high number of exhausted cytotoxic T cells infiltrating the marrow (tumor) prior to therapy.(80) It has also been shown that tumor infiltrating lymphocytes that express the highest frequency T cell receptor beta chain clonotypes are tumor specific.(84) Thus, we will use T cell receptor beta chain complementarity-determining region 3 (TCRB CDR3) region sequencing (ClonoSeq, Adaptive Biotechnologies) to identify clonally-expanded, tumor specific lymphocytes in the marrow prior to HLA-mismatched CD4+ DLI and will confirm that the T lymphocytes that become activated after HLA-

mismatched CD4+ DLI share the same TCRB signatures and, thus, are also tumor specific. TCRB signatures will also be compared between responders and non-responders to support that clinical remissions are due to clonal T cell expansion rather than just a chemotherapy effect.

# Aim 3: In patients with MDS/AML who received HLA-mismatched CD4+ DLI therapy, characterize cytokine profiles from the blood associated with severe cytokine release syndrome.

#### Plasma Cytokine Profile

HLA-mismatched CD4+ DLI is expected to reverse immune exhaustion and stimulate an inflammatory response consistent with cytokine release syndrome (CRS), characterized by fevers and sometimes associated hypotension or hypoxia.(85) Thus, we aim to identify risk factors for severe CRS in patients treated with this novel therapy. Clinically, we will compare baseline variables of patients who experience severe CRS and those who do not, including HLAmismatched CD4+ DLI dose, degree of HLA mismatch, choice of induction chemotherapy, and disease burden, all factors that are predictive of CRS with other cell therapies. (86-88) In the setting of chimeric antigen receptor T cells (CAR-T) therapy, confirmation that CRS is correlated with high levels of interleukin-6 (IL-6) led to the effective use of IL-6 blockade as CRS treatment.(89-91) We will similarly evaluate cytokine profiles associated with CRS to identify potential targets for anti-CRS therapy. As CRS typically occurs in the first 7 days after other cell therapies, we will collect blood samples prior to therapy and then daily from the day of HLAmismatched CD4+ DLI infusion through day 7 after infusion. We will test plasma using the Ella multiplex cytokine assay to identify the T cell-derived cytokines (e.g., IFN-gamma, IL-6, IL-17, TNF-alpha) increased at baseline in patients who develop severe CRS and monitor which cytokines significantly increase with onset of CRS. For patients who experience CRS, we will also monitor changes to the cytokine profile after administration of IL-6 blockade (tocilizumab) and correlate temporally with clinical resolution. The association between severe CRS and clinical variables (e.g., DLI dose, degree of HLA mismatch, choice of induction chemotherapy, disease burden) and the change of cytokine profiles after treatment (e.g. IFN-gamma, IL-6, IL-17, TNFalpha) will be explored by the Satterthwaite t-test. Specifically, cytokine profiles will be measured at baseline, and days 0 through 7. The GEE model may be employed to assess change over time in the difference between two groups. Odds ratios will be estimated along with 95% confidence intervals by using the simple logistic regression or the GEE model. Other statistical considerations apply as discussed in Aim 2. These studies will confirm whether IL-6 is primarily implicated in causing toxicity with HLA-mismatched CD4+ DLI or if other cytokines may be more effective targets for managing this toxicity.

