
### Power calculations

We expect up to 18 subjects will be enrolled in this phase I with cohort expansion study. For Aim 1, up to 18 subjects will have 80% and 98% power to detect an effect size of 0.7 and 1.0 at a two-sided significance level of 5%. The one-sample t-test is used. For Aim 2 and 3, the maximum power is obtained when the sample size of two groups is identical (i.e., 9 subjects per group). For each endpoint of Aim 2 and 3, the study will have 85% power to detect an effect size of 1.5 at a two-sided significance level of 5% when sample size of each group is 9. If the sample

size of one group deviates from 9, the statistical power will decrease, accordingly. Two sample t-test is used for Aim 2 and 3, and no multiplicity adjustment is considered for power analyses.

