# 9.4.2 ANALYSIS OF THE PRIMARY ENDPOINT(S)

For the dose escalation portion, a minimum of two subjects and a maximum of 18 subjects will be enrolled. There will be three dose levels in the dose escalation portion. MTD is defined as the highest dose level with the probability of DLT less than 33% (DLT events are defined in Section 6). The DLT observation window will be until confirmation that the donor cells have been rejected (ANC ≥ 500/microL AND confirmation of either bone marrow donor chimerism <5% or donor blood CD3+ chimerism <5%) OR within 56 days following NE-DLI, whichever occurs first. Per the traditional 3+3 schema, up to three patients may be enrolled concurrently and treated at the same dose level. The first three patients will be treated at dose level 1. For each dose level, if none of three patients experiences a DLT, we will escalate to the next dose level until reaching dose level 3. For each dose level, if one of the three patients experiences a DLT, we will enroll three additional patients and treat at the same dose level. In this case, if none of these additional three patients experiences a DLT, we will escalate the dosage to next level until reaching dose level 3. For each dose level, if two or more patients among six enrolled patients experience a DLT, or two or more patients in the three patient cohort experience DLT, the dosage level exceeds the MTD and the previous dose level will be declared as the MTD. If the first dose level exceeds the MTD, the study will be suspended. If no subjects experience a DLT at any dose level, the MTD will be level 3 (5 x 10^7 CD4+ T cells/kg). Similarly, if exactly one of six patients enrolled at dose level 3 experiences a DLT, then the MTD will be dose level 3. All patients in a dose level must be observed through the DLT window prior to enrolling patients at a higher dose level.

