# 9.4.3 ANALYSIS OF THE SECONDARY ENDPOINT(S)

The RP2D is defined as the dose level selected to be evaluated in the expansion cohort or future phase II studies and will be equivalent to the MTD determined in the Phase 1b portion of the study. Once we determine the RP2D level, we will enroll 10 additional eligible patients and treat with the RP2D level. The goal for this expansion cohort is to evaluate the safety and tolerability for patients who will be treated with NE-DLI in the RP2D dose level, and to evaluate the preliminary efficacy estimate for the ORR. Including the dose escalation portion in which 3 or 6 enrolled patients will have been treated at the RP2D level, a total of at least 13 patients will be treated at the RP2D level. Based on previous data, (99) the complete response rate using microtransplantation was in the range of 36%-52% for MDS or AML from antecedent MDS patients. Hence, for the phase 2 portion, an ORR of 45% is considered clinically meaningful. With a sample size of 13 patients, if our ORR is 45%, the 95% CI (exact binomial) will be (18-74%); if the ORR is 50%, the 95% CI will be (22-78%). The response rates, including ORR and hematologic response by IWG 2006 criteria will be estimated via an exact binomial test with 95% confidence interval in combining patients treated at the RP2D dose level and the expansion cohort patients.

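### Aim 3 tests DLI dose against severe CRS with a Satterthwaite t-test, which is invalid when the few severe cases all share one of only three doses

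*Combined protocol and SAP*

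**What the plan says.** Aim 3 in section 8.3.1 sets out to find risk factors for severe CRS. It will "compare baseline variables of patients who experience severe CRS and those who do not". The text reads "The association between severe CRS and clinical variables (e.g., DLI dose, degree of HLA mismatch, choice of induction chemotherapy, disease burden"), together with changes in cytokine profiles, "will be explored by the Satterthwaite t-test". Odds ratios from simple logistic regression or GEE are also planned. Aim 3 adopts the statistical considerations of Aim 2: the work is exploratory, there are no multivariable models and no multiplicity adjustment, and Wilcoxon tests are an optional secondary approach.

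The power paragraph at the end of 8.3.1 claims "85% power to detect an effect size of 1.5 at a two-sided significance level of 5% when sample size of each group is 9". It treats unequal group sizes only as a loss of power.

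Other sections determine how doses are filled:
- Section 6.1.2.3 gives three levels: 1 x 10^6, 1 x 10^7 and 5 x 10^7 CD4+ T cells/kg.
- Section 6.1.4 includes "Grade 3-4 cytokine release syndrome (CRS") among the DLTs.
- Section 9.4.2 stops escalation "if two or more patients among six enrolled patients experience a DLT, or two or more patients in the three patient cohort experience DLT".
- Section 9.4.3 adds: "Once we determine the RP2D level, we will enroll 10 additional eligible patients and treat with the RP2D level".

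**The concern.** The Satterthwaite t-test compares mean dose between patients with and without severe CRS. It needs a usable variance estimate from each group. Here the outcome is rare, the variable has three values, and the design concentrates patients at one level. Two or three severe cases will often all have the same dose. Their estimated variance is then zero, and the test treats their mean dose as if it were known without error. If that shared dose is the top one, any patients treated at lower levels pull the non-severe mean down, and the test can reject although risk does not depend on dose.

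A second feature adds to this. Grade 3-4 CRS is a DLT, so CRS outcomes help decide which doses are filled.

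At stake is a reported association in one direction (more severe CRS at higher dose) that the design can produce on its own.

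**Working it through.** **The plan's own figure.** Two-sample t-test, d = 1.5, 9 per group, two-sided 5%: noncentrality 1.5 x sqrt(9/2) = 3.18 on 16 df gives power 84.8%, so the stated 85% reproduces. It rests on 9 versus 9. With 19 patients (3 + 3 + 13) and a severe-CRS rate of 10% to 15%, the expected number of severe cases is 19 x 0.10 = 1.9 to 19 x 0.15 = 2.9.

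**One worked table.** Take 0/3, 0/3 and 2/13 severe cases at levels 1, 2 and 3, with dose as log10 (6, 7, 7.699).
- Severe group: n = 2, mean 7.699, variance 0.
- Non-severe group: n = 17, mean (3 x 6 + 3 x 7 + 11 x 7.699)/17 = 7.276, SD 0.665.
- t = (7.699 - 7.276)/sqrt(0/2 + 0.665^2/17) = 0.423/0.161 = 2.62. The Satterthwaite df reduce to 17 - 1 = 16, so p = 0.018.
- If two cases fall at random among 19 patients, both are at level 3 with probability (13 x 12)/(19 x 18) = 46%. The exact conditional trend test gives two-sided p = 0.75.

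A result that chance produces almost half the time is declared significant.

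**Whole-trial error rate.** Inputs from the documents: the 9.4.2 rule, 10 further patients at the MTD, and the Table 1 limits in 9.4.4 (2 DLTs at 3 patients, 3 at 4-6, 4 at 7-10), checked after 3 patients and then every 2. Assumptions:
- severe CRS means grade 3-4, since Aim 3 does not define it
- its true rate is equal at every dose
- it is the only DLT
- a Table 1 hold ends accrual
- a trial where the test cannot be computed counts as no finding

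Share of simulated trials (25,000 per row) with p < 0.05 and higher dose in the severe group; the nominal share in that direction is 2.5%:

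| True severe-CRS rate | 9.4.2 rule | 9.4.2 rule, CRS labels shuffled within trial | RP2D first filled to 6 (6.1.4) |
|---|---|---|---|
| 3% | 5.4% | 3.6% | 7.1% |
| 5% | 11.2% | 7.1% | 14.4% |
| 10% | 20.5% | 11.9% | 23.8% |
| 12% | 21.5% | 12.0% | 23.3% |
| 15% | 20.9% | 11.0% | 21.8% |
| 20% | 15.9% | 7.9% | 15.6% |
| 30% | 6.7% | 2.9% | 5.9% |

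Exact enumeration of the 9.4.2 rule agrees: 20.7%, 20.8%, 16.2% and 10.9% at rates of 10%, 15%, 20% and 25%, then 4.0% at 35% and 2.3% at 40%. Untransformed dose gives similar results. The exact conditional trend test rejects in about 2% of the same trials at rates of 10% to 25%.

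**Source of the error.**
- Near the peak, at least 95% of false positives have zero dose variance in the severe group.
- A fixed 3/3/13 allocation with no adaptation still rejects in 21% to 24% of trials at rates of 10% to 20% (both directions). A fixed 6/6/6 allocation rejects in 7% to 8%.
- Shuffling CRS labels within each trial keeps the allocation but breaks its link to outcomes. The peak falls from 21.5% to 12.0%, so outcome-driven assignment adds about 9 points, a little under half.

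**Sensitivity.** If other DLTs occur at 10%, the peak is about 12-13%. The power paragraph says "We expect up to 18 subjects will be enrolled in this phase I with cohort expansion study", whereas section 4.4 allows 28; using only the first 18 patients, the peak is about 20%.

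**The case against.** The strongest reply is that this is one exploratory correlative analysis, run only if funding permits, in a plan that speaks of association and also offers odds ratios and Wilcoxon tests. Much of that stands, and it limits the importance of the point. It does not rescue the test. The exploratory label is used to waive multiplicity adjustment, not to excuse one test running far above its level in one direction. The Wilcoxon option lowers the false-positive rate to at most about 8% in the same simulations, but it is optional. When all severe cases sit at the top dose, as in the worked table, the simple logistic odds ratio has no finite maximum-likelihood estimate.

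A reader might infer four stronger things that the documents do not support:
- **That the error is generally 1 in 4.** That needs the 6.1.4 refill to 6, a rate near 10% and no other DLTs. Section 6.1.4 lists several other DLT types.
- **That the 3+3 rule's response to CRS is the main cause.** Fixed 3/3/13 allocation produces about the same error.
- **That a false result would misdirect dose selection.** Sections 4.3 and 9.4.3 set the RP2D equal to the MTD from the DLT rule, including for future phase II studies. This p-value plays no part.
- **That the plan claims dose causes CRS.** It does not.

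Treating a Table 1 hold as final is also an assumption, because 9.4.4 says only that enrollment is held for review of the MTD.

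**Conclusion.** The point holds as a defect in one named exploratory test. For DLI dose, the Satterthwaite t-test is unreliable under this design, mainly because a few severe cases share one dose under lopsided allocation; outcome-driven dose assignment makes it worse. With equal risk at every dose, no other DLTs and final holds, false higher-dose findings peak at about 1 trial in 5 under 9.4.2 (up to 24% with the 6.1.4 refill). They stay well above nominal at a 5% or 25% rate (about 11%) and fall below 5% from 35% upward. Because the documents give no severe-CRS rate, these figures are a range and not a prediction. The MTD, the RP2D and the primary and secondary endpoints are untouched. The change is worth making because it costs almost nothing.

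**What to change.** In section 8.3.1, Aim 3:
1. Remove DLI dose from the variables tested by the Satterthwaite t-test.
2. Report the number of severe CRS cases over patients treated at each dose level, with exact binomial confidence intervals.
3. If a p-value is wanted, use an exact conditional (permutation) trend test on the dose-level counts. State that it is conservative, has little power, and is only approximately valid when outcomes drive allocation; it can be calibrated by simulating the escalation rule.
4. Label any dose comparison or dose odds ratio as descriptive.

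The cost is a wording change and a table from data already collected, with no extra patients or visits. The real price is less apparent power for the dose association. In the worked table, two cases at the top level are already the most extreme upward result possible, and the exact test still gives p = 0.75. That is why description comes first.
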